### **3.3 Study Design**

#### **3.3.1 Basic PRODUCE Study Design:**

This study will employ a series of individual N-of-1 trials that compare the SCD to a modified SCD using a collaborative approach between patients, parents, and their clinical team. Patients will enter the study on a usual (non-SCD) diet and will have a minimum 1-week run in period for diet planning and baseline data collection before beginning their assigned treatment. Treatment periods will be assigned in blocks of two (e.g., AB) with the goal of each patient completing two balanced treatment blocks (e.g., ABAB) where treatment 'A' represents SCD and treatment 'B' represents modified SCD. Patients will be randomized to either the SCD or modified SCD as their starting intervention and alternate between these two conditions for four 8-week treatment periods. The study design is summarized in Figure 1.

**Figure 1**

By completing an N-of-1 study, each individual will have a personalized answer regarding the comparative effectiveness between a highly restrictive diet (SCD) and a more broadly sustainable middle ground option (modified SCD) as compared to their baseline diet. In addition, we will aggregate the results of the completed N-of-1 trials across all patients to estimate the population level comparative effectiveness of these dietary treatments and the effectiveness of each compared to a typical, non-SCD, diet. As there is uncertainty regarding whether the sequencing of the intervention is important (e.g., whether patients must initiate a full SCD diet before modifying the diet to be less restrictive), we opted to randomize the initial treatment to be able to examine whether effects differ based on the initial diet type. Although using an ABAB/BABA design without randomization of treatment periods may result in patients anticipating their next intervention period, we do not believe this will result in increased dropout rates or failure to complete all treatment periods because patients and parent stakeholders expressed that they are interested in testing both diets—those who improve on SCD will be interested in determining whether they can maintain improvements on the modified SCD and those who improved on the liberal SCD will be interested in determining whether they can achieve greater improvements on a more strict SCD. The rationale for the duration of each treatment period (8-weeks) was based on the concern that patients would be unlikely to stay on a diet for more than 8 weeks if they did not observe a benefit and based on information from *Breaking the Vicious Cycle* and preliminary studies from research co-investigators indicating the symptoms improve within ~1 month and markers of inflammation by 2 months.

### 3.3.2 Technology Platform Configuration

Study participants will use the Eureka N-of-1 platform (website and mobile app) to execute the research proposed in this study. The Eureka N-of-1 platform will enable participants and their clinicians to collect outcome data, track intervention/exposure status, and review collected data in real time. Upon trial completion, Eureka will present N-of-1 results to patients and providers with easy-to-understand graphics that include probabilistic assessments of the benefits of the

## USING SINGLE SUBJECT (N-OF-1) DESIGNS TO ANSWER PATIENT-IDENTIFIED RESEARCH QUESTIONS – AIM 1

intervention. Eureka will configure a study-specific version of the platform to execute the research proposed in this study. Screen shots of the Eureka app are provided in Appendix A.

The Eureka Research Platform is a digital research platform developed at the University of California San Francisco as part of a cooperative agreement with the National Institutes of Health. The purpose of the platform is to facilitate mobile health research for any interested investigator. The Eureka platform includes a participant-facing “front end,” with mobile app and web-based interfaces, an investigator portal, and a secure “back end” for data storage and analyses. The platform is designed as an all-inclusive, configurable, easily-scalable research platform, inclusive of all aspects of research—from participant enrollment, onboarding and consent, to multi-modal data collection, study administration/management, and data extraction. The platform’s front end can be customized by individual investigators to implement their specific research project. Existing functionality includes the ability to obtain remote consent (although in-person consent can also be used), deploy participant surveys, message participants via push notifications, texts, or emails, integrate with external apps, sensors, and Bluetooth enabled devices, and capture data collected from smartphones (such as geolocation data or accelerometer/ activity data). The investigator portal provides a secure website wherein investigators, coordinators or other individuals with appropriate permissions can visualize relevant participants’ data and study status. The back end of the Eureka platform is a multi-tenant system that enables data collection, management and storage derived from multiple sources and from studies of various forms. This architecture rests on a secure and HIPAA-compliant Amazon Web Services (AWS) cloud with the capacity to curate dense data from more than 1 million participants. In addition to providing data as needed to investigators, the infrastructure houses a de-identified data repository that is publicly available to help fulfill the general mission of advancing science and wellness.

As part of design sessions held prior to enrollment, members of the research team including patients, parents, and clinicians will provide input regarding the study-specific configurations of the Eureka platform. Study specific configurations will include: (1) trial specific onboarding page, (2) code to generate and perform analyses of trials based on a trial-specific template, (3) server workflow that automates execution of the personal trials, and (4) customization of the user interface for prompts, reminders, forms, surveys, and visualizations. Final configurations will depend on input from key stakeholders. Technology modifications will be done via iterative, rapid development and testing cycles

### 3.3.3 Interventions and Comparators

The diets are defined as follows:

1. Usual Diet (Baseline Condition): Patient eats a typical, non-SCD, diet. Diet may include some restrictions (which is common in IBD) such as seeds/nuts or gluten, but exclusions will not be as broad as with the SCD and Modified SCD (e.g., patient still eating grains and/or dairy). May include full or partial exclusive enteral nutrition as the currently available liquid supplements are not SCD compatible.
2. Specific Carbohydrate Diet (SCD): The dietary program will follow recommendations outlined in *Breaking the Vicious Cycle* by Elaine Gottschall. Allowed foods include meat/fish/poultry, eggs, some legumes (e.g., lentils and split peas are permitted, chickpeas and soybeans are not), fully fermented yogurt, non-starchy vegetables, ripe fruit, nuts/seeds, honey and nut flours (e.g. almond flour or coconut flour). SCD compatible vitamins are allowed and will be recommended on as needed basis by study dietitians. Restricted foods include all grains, milk

products aside from 24-hour fermented SCD yogurt and cheeses aged greater than 30 days, starchy vegetables, processed foods with food additives and sweeteners other than honey.

3. **Modified Specific Carbohydrate Diet (SCD):** A more liberal, and thus, perhaps more sustainable version of the SCD. In addition to the foods in the SCD, allowed foods will expand to include organic rice, oats, sweet potatoes, Grade A maple syrup and 100% unsweetened cocoa powder (not Dutch processed) or 100% cacao powder, nibs, or butter (no sugar added) for this group. For oats, organic rice, and sweet potatoes, patients will be instructed to consume a minimum of 3 servings and a maximum of 6 servings of any combination of these items per week. On any given day, they should not have more than 2 servings of any combination of these items. A serving size is 1 cup. For maple syrup and 100% unsweetened cocoa powder (not Dutch processed) or 100% cacao powder, nibs, or butter (no sugar added), patients will be asked to consume a minimum of 2 Tablespoons of each item per week and a maximum of  $\frac{1}{2}$  cup of each per week. The reasons for the minimum amount of these food items each week is to distinguish the diet from the SCD enough to provide a useful comparison. Gluten, corn products, milk products (except yogurt and aged cheeses), sweeteners (except honey), and process foods will still be restricted.

### **3.4 Study Procedures**

**Baseline evaluation:** Study participants will complete a routine clinical assessment including disease activity measures and standard lab tests that assess inflammation and disease status (per center standard of care). Participants must have documented evidence of acute inflammation and/or elevated acute phase reactant as measured by Fecal calprotectin 1.5 times the upper limit of normal, Lactoferrin 1.5 times the upper limit of normal, CRP 1.15 times the upper limit of normal, or ESR 1.15 times the upper limit of normal (based on local reference ranges) within 8 weeks of enrollment. Potential participants who are close to meeting one of the acute inflammation and/or elevated acute phase reactant markers and who meet all other study criteria will be considered for study participation on a case by case basis by the investigative study team in consultation with the patient's primary gastroenterologist. A stool sample for fecal calprotectin and banking for microbiome analysis will be collected by the patient at home and sent in for analysis. A trained dietitian will provide 1:1 diet training and resources, including print and web-based materials (Appendix B). The dietitian will send the participant home with a 3-day diet recall to be returned to clinic (see process outlined in section on "Diet Monitoring"). In the event that the site dietitian is unavailable for the baseline training, it may be conducted by the site coordinating center dietitian via video call (i.e., Zoom, Skype) if permission is granted by the patient's primary GI physician or advanced care provider. Patients and parents will be trained in the use of the Eureka N-of-1 app. Participants will be randomized to either the SCD or modified SCD as their starting intervention with a 1:1 allocation ratio. We will utilize a centralized, stratified, block randomization approach. We will stratify within sites and by disease type (UC/IC or CD). Patients and parents will also complete psychological assessments and questions regarding their baseline expectation of benefit related to diet (see Table 1, Appendix C) via paper, tablet, website, or Eureka app at the baseline visit. Following the baseline evaluation, participants will spend a minimum of 1 week (maximum of 4 weeks) collecting baseline data and preparing to begin their first assigned diet treatment. They will be asked to not change their diet until they begin their first treatment period. The baseline period is defined as the period from enrollment to the start of the N-of-1 trial (1- to a maximum of 4 weeks).

**Diet Staging:** At the start of the initial diet treatment block (either SCD or modified SCD), participants will gradually transition from their usual diet to their initial diet intervention. For

## USING SINGLE SUBJECT (N-OF-1) DESIGNS TO ANSWER PATIENT-IDENTIFIED RESEARCH QUESTIONS – AIM 1

patients randomized to the SCD, they will restrict their diet to the most easily digestible foods such as broths, fruit juice, ripe, peeled and cooked fruits, squash and carrots, and non-fried lean meat, fish, poultry and eggs for the first 2-3 days. After this initial step, participants will expand their diet to include all remaining SCD approved foods. For patients randomized to the modified SCD, for the first 2-3 days, they will restrict their diet in the same manner as those randomized to the SCD. Then, they will expand their diet to include all remaining SCD approved foods for another 2-3 days before adding the additional foods allowable on the modified SCD. Thus, by 5-7 days into the treatment, participants randomized to start with the modified SCD will have advanced to the full modified SCD diet.

Follow Up contact: Based on standard of care for initiating a new dietary treatment, patients will be evaluated by the dietitian and/or physician or advanced practice care provider (i.e., nurse practitioner or physician's assistant) at  $2 \pm 1$  weeks after starting each new diet. This visit may be completed by phone call, video call or telemedicine visit, per the discretion of the primary GI physician or advanced care provider. If this appointment does not take place in-clinic, it is the site's research staff's responsibility to make sure that the patient's weight is obtained using the same scale at every weigh in and that the patient reports the measured weight to the study staff. Participants will also have a phone or in-person follow-up with either their site's dietitian or the site coordinating center dietitian in each treatment period. The dietitian will evaluate patient weight (on clinic scale at follow up visits and if available by home scale) and nutritional intake. S/he will prescribe SCD compatible nutritional supplements as needed based on review of the diet recall. In addition, at the clinic visits, follow up phone calls or visits, and during any other patient contact, the dietitian will carry out standard of care activities including, but not limited to, evaluating the participant's nutrition and overall health, assessing the participants nutritional and dietary needs, providing diet advice, sharing sample meal plans, developing new meal plans, and sharing recipes from books, online resources, or other personal sources. In the event that the site dietitian is unavailable for follow-up contact, these visits may be conducted by the site coordinating center dietitian via video call (i.e., Zoom, Skype) if permission is granted by the patient's primary GI physician or advanced care provider.

Symptom tracking: Participants will use the Eureka N-of-1 mobile app to execute the N-of-1 protocol, track treatment periods, and track daily and weekly symptoms and disease activity. Participants and their clinician will be able to visualize the tracked data in real-time via the Eureka N-of-1 app and on the web portal. Parents of participants will always track symptoms using the mobile app. Patients  $\geq 14$  to 18 years will have the option of tracking for themselves (in addition to their parent). Patients  $< 14$  years will have parents track for them with child input. The questions to assess symptom and disease activity metrics are included in Appendix D. Participants will be asked to start tracking at the baseline visit. Patients will be asked to complete a minimum of 2 weeks of symptom tracking in the baseline period (14 daily measures, 3 weekly measures) and will be asked to continue with tracking once they initiate the N-of-1 Trial via the Eureka app.

Stool Collection: Participants will collect a home-based stool sample for fecal calprotectin analysis and biobanking for future analysis during the baseline period and the end of each treatment period. Stool specimens will be accepted as early as up to 2 weeks before the end of the treatment periods. Active participants will not be able to advance to their next treatment block until stool is collected and sent. If a patient elects to terminate a treatment condition early, they will be asked to submit a stool specimen at that time, prior to changing treatment conditions. Participants who discontinue the study after the first crossover (e.g., completion of baseline, Diet A1, and Diet B1) and terminate the protocol early may advance to the end of the study without additional stool collection. Patient instructions for stool collection are documented in Appendix E. Fecal

## USING SINGLE SUBJECT (N-OF-1) DESIGNS TO ANSWER PATIENT-IDENTIFIED RESEARCH QUESTIONS – AIM 1

calprotectin results will be made available to the clinicians as the results are returned from the lab.

**Clinical Evaluations:** Participants will be seen for clinic visits as needed throughout the study. Based on standard of care for initiating a new dietary intervention and the fact that patients enrolled in this study have mild or moderate disease activity, close follow up is recommended. Participants will have a follow up visit  $8 \pm 2$  weeks from initiation of the first diet period and then as needed over the remainder of the study, with timing based on each individual center's standard practice and patient need. This pragmatic design allows us to test the use of the N-of-1 methodology for diet intervention as it would be delivered in regular clinical care. Data collected at routine clinic visits is standardized and includes weight, height, current medications, laboratory assessment, and disease activity (PUCAI and SPCDAI). This data is entered in the ICN registry. Assessment of Vitamin D levels is performed per local site standard of care. This data is not collected in the ICN registry. The date and results of all Vitamin D levels collected at regular clinical evaluations will be entered in the REDCap database by the research coordinator or dietitian at each site.

[figure not shown]
**Diet Monitoring:** Patients will complete a 3-day diet diary at baseline and during each diet period, ideally around the mid-point of that period (approximately 3-5 weeks after transitioning to the new diet). The questions that will be used in the 3-day diet diary are included in Appendix F. The participant will return their completed diet diary to the local center dietitian or research coordinator via email/scan/text/mail. Once received from the patient and verified for completeness, the center dietitian or research coordinator will email the patient's completed 3-day diet diary to the study's central email at CCHMC and it will be triaged to approved research staff at Seattle Children's Hospital all using a secure and IRB-approved email system. The research staff member at Seattle Children's Hospital will enter the data from the 3-day diet diary into a nutrient composition program. Output from the nutrition composition program (e.g., total calories, percent calories from fat, percent calories from carbohydrates, percent calories from protein, micronutrient composition) will be communicated back to the patient's site dietitian (using IRB-approved communication channels) and will be entered into a REDCap database by the research staff at Seattle Children's Hospital or exported electronically and sent to CCHMC. The site dietitian or site coordinating center dietitian (if local dietitian is unavailable) will follow up with the patient via telephone or in-clinic to discuss any issues with the diet, discuss nutritional adequacy of diet, and recommend any adjustment in dietary intake or vitamin supplements. The dietitian will continue to attempt contact until the participant is reached.

**Study Completion and N-of-1 Results Review:** Following the final treatment period, participants will return to clinic within 4 weeks to complete a standard physical exam including weight, height, medications, and clinical measure of disease activity. They will review the results of their trial via the Eureka N-of-1 platform with their clinician (Appendix G) and will complete a final questionnaire regarding their experience with the N-of-1 trial via tablet, website, Eureka app, or paper. If the final results review is unable to be conducted in person with the study physician, the results can be provided via phone call, video call or telemedicine visit, per the discretion of the primary GI physician or advanced care provider. If the results are provided virtually, the site is still required to schedule an in-person clinician visit to complete a standard physical exam with the participant.

The overall study procedure timeline is summarized in Figure 2.

### Figure 2\*

# USING SINGLE SUBJECT (N-OF-1) DESIGNS TO ANSWER PATIENT-IDENTIFIED RESEARCH QUESTIONS – AIM 1

\*This figure is an approximate representation of the typical time it would take for a participant to finish the study.

Patients will be supported in their adherence to the diet through a variety of means. Dietitian/physician or advanced practice provider involvement and follow-up (as described above) is a key component to providing supportive coaching for patients and families. In addition, resources, including print and web-based materials (Appendix B), will be made available for patients to support them in learning about the diet, provide ideas for meal planning, offer approaches for teaching other family members and friends about the SCD, handling family gatherings and special occasions, etc.

## Outcome Measures

Study outcomes and mediating factors are detailed in Table 1. Primary outcomes across all patients will include patient reported outcomes (PROs) of stool frequency, stool consistency, pain interference and GI symptom severity (see Appendix D), and fecal calprotectin. Secondary outcomes will include patient-reported disease activity scores as measured by the Pediatric Ulcerative Colitis Activity Index (PUCAI) and Short Crohn's Disease Activity Index (SCDAI), clinically-evaluated disease activity scores contained in ICN registry (PUCAI and sPCDAI), growth, laboratory markers of inflammation and disease status [C Reactive Protein (CRP), Hematocrit, Erythrocyte Sedimentation Rate (ESR), Albumin]. Fecal calprotectin was selected as the central marker of intestinal inflammation because it correlates well with both clinical and histologic remission, is noninvasive and objective, and has been shown to be a useful tool to monitor response to therapy. Safety Outcomes: The major safety concerns for patients with IBD participating in a diet intervention include weight loss and inadequate nutrition. Weight loss typically occurs within the first few weeks of starting the diet. Weight will be assessed at all clinic visits and at the dietitian follow up visits (weeks 4 and 12) and by weekly weights entered in the Eureka app if there is a home scale available. If a home scale is available, patients will be instructed to obtain an initial weight on their home scale at the beginning of the baseline period and use the same home weighing scale throughout the study period. Nutrition intake will be monitored by the dietitian regularly for all enrolled patients and will be assessed via 3-day diet diaries conducted at specified intervals (baseline and in weeks 3-5 of each treatment period) and weekly weight tracking (if available). In addition, we will collect results of any serum Vitamin D level monitoring conducted as part of routine care and will report these results to the DSMB. Mediating factors: We will collect demographic data from the ICN registry including age, gender,

## USING SINGLE SUBJECT (N-OF-1) DESIGNS TO ANSWER PATIENT-IDENTIFIED RESEARCH QUESTIONS – AIM 1

race, ethnicity, family education level, disease type, disease location, medications, and disease characteristics at baseline. Dietitians will use data from 3-day diet diaries to assess deviation from the prescribed diet (Appendix F). We will also measure the patient and parent psychological well-being and expectations regarding benefit of diet as a treatment strategy as these may mediate adherence to the diets.

If a measure is missing in any of the sources listed below, we will obtain the data using other sources which could include secured email correspondence with the site and/or screening and eligibility verification case report forms. The screening and eligibility verification case report form is a non-patient facing tool currently used by the site coordinator to verify participant eligibility. This form is uploaded to OneDrive so that the site coordinating center can confirm eligibility; thus, it is data the site coordinating center already routinely receives.

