**Table 1: Outcome Measures**

Construct	Measure(s)	Timing	Source
OUTCOMES			
Stool Frequency	Single integer count	Daily	N-of-1 App
Stool Consistency	Bristol Stool Scale 	Daily	N-of-1 App
Pain Interference	PROMIS® Pain Interference 	Weekly	N-of-1 App
IBD Severity	PROMIS® Gastrointestinal (GI) Symptoms*	Weekly	N-of-1 App
Growth	Weight †	Weekly	N-of-1 App
Self-Report Disease Activity	Pediatric Ulcerative Colitis Activity Index (PUCAI)  Short Crohn's Disease Activity Index (sCDAI) 	Weekly	N-of-1 App
Intestinal Inflammation	FecalCalprotectin	Baseline and at the end of each treatment period	Lab
Disease Activity	sPCDAI  , PUCAI 	Sporadic, Clinic Visits	Registry
MEDIATORS			
Psychological Well-being (Parent)	PROMIS® Anxiety PROMIS® Depression	Baseline	Web-survey or N-of-1 App
Psychological Well-being(Child)	PROMIS® Anxiety PROMIS® Depression	Baseline	Web-survey or N-of-1 App
Expectations of Benefit	Treatment expectations and preferences (adapted from published study) 	Baseline	Web-survey or N-of-1 App

\*Measure was validated in a sample of 1,007 children and youth in ICN ages 8-24. The scale exhibits acceptable internal consistency with a Cronbach's alpha of 0.74. The measure is highly responsive to differences in clinical status as assessed by both the patient and their physician/advanced practice care provider using validated measures and produces reliable estimates of GI symptom T-Scores ranging from 45 to 80.

†Optional, only if home scale available

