#### **3.5.1 Inclusion Criteria**

- Diagnosis of CD or UC or Indeterminate colitis (IC)
- Age 7-18 years
- Enrolled in the ImproveCareNow ICN2 registry; and

- Evidence of acute inflammation and/or elevated acute phase reactant as measured by Fecal calprotectin 1.5 times the upper limit of normal, Lactoferrin 1.5 times the upper limit of normal, CRP 1.15 times the upper limit of normal, or ESR 1.15 times the upper limit of normal (based on local reference ranges) obtained within 8 weeks of enrollment.
  - Potential participants who are close to meeting one of the acute inflammation and/or elevated acute phase reactant markers and who meet all other study criteria will be considered for study participation on a case by case basis by the investigative study team in consultation with the patient's primary gastroenterologist.

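### The missing-measure fallback lets an eligibility calprotectin value replace the baseline stool sample; where that value qualified the patient, regression to the mean inflates that patient's diet-versus-usual-diet result

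*Combined protocol and SAP*

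**What the plan says.** The fallback stands directly above Table 1: "If a measure is missing in any of the sources listed below, we will obtain the data using other sources". The examples it gives of such sources are site email and the "screening and eligibility verification case report forms". It is worded as what the study will do, not as an option. It names no measure, time point, date window or laboratory, and asks for no flag or sensitivity analysis.

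Table 1 lists fecal calprotectin with the timing "Baseline and at the end of each treatment period" and the laboratory as source. The same section makes it a primary outcome: "stool frequency, stool consistency, pain interference and GI symptom severity (see Appendix D), and fecal calprotectin".

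Section 3.4 plans the baseline value as a stool sample collected at home during the baseline period, which runs from enrollment to the start of the N-of-1 trial and lasts 1 to 4 weeks.

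The eligibility value is a different measurement. Section 3.5.1 admits patients on "Evidence of acute inflammation and/or elevated acute phase reactant as measured by Fecal calprotectin 1.5 times the upper limit of normal", or on lactoferrin, CRP or ESR, read on local reference ranges and "obtained within 8 weeks of enrollment". Near-misses may be admitted case by case.

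Section 3.6.2 gives each patient the difference between each diet and baseline and the probability that each diet is better than baseline. The pooled model includes baseline levels so that each diet can be compared with the unrestricted diet.

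**The concern.** An eligibility calprotectin differs from the planned baseline in three ways.

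- **Selection.** If calprotectin was the qualifying marker, the value was accepted because it was high. Part of that height is short-term variation that will not recur.
- **Age.** It can predate enrollment by weeks, and the baseline period adds more.
- **Source.** It was judged on local ranges and may come from a different assay or laboratory than the home sample sent in for the study.

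Only one baseline calprotectin is planned, so a substituted value is that patient's whole baseline. Regression to the mean would then look like improvement on both diets, on the marker the protocol chose for its objectivity. The results display (Appendix G) reports the chance that each diet beats the usual diet, and families would weigh that against the burden of the diet.

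**Working it through.** The plan has no figure of its own to reproduce here. Its power statement (section 3.6.1) concerns PROMIS pain interference and does not bear on this point.

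**Age of the value.** Up to 8 weeks before enrollment (3.5.1) plus up to 4 weeks of baseline period (3.4): 8 + 4 = 12 weeks before the first diet.

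**Regression to the mean.** Take log calprotectin as normal with standard deviation SD, a qualifying cut c standard deviations above the mean of those screened, and correlation r between the eligibility value and the later value. With no diet effect:

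- expected fall in log units = (1 − r) × SD × λ(c), where λ(c) = φ(c) / (1 − Φ(c));
- apparent percentage fall = 1 − exp(−fall).

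λ(0) = 0.798, λ(0.5) = 1.141, λ(1) = 1.525. SD, r and c are all assumed.

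| Set A (assumed) | Log fall | Apparent fall |
|---|---|---|
| SD 0.8, r 0.8, c 0 | 0.2 × 0.8 × 0.798 = 0.128 | 12% |
| SD 0.8, r 0.65, c 0.5 | 0.35 × 0.8 × 1.141 = 0.320 | 27% |
| SD 1.2, r 0.65, c 0.5 | 0.35 × 1.2 × 1.141 = 0.479 | 38% |
| SD 1.2, r 0.5, c 1 | 0.5 × 1.2 × 1.525 = 0.915 | 60% |

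Set B assumes SD 1.0 to 1.5, a constant correlation of 0.5 to 0.8, and 30% to 80% of screened values above the cut.

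| Set B (assumed) | Log fall | Apparent fall |
|---|---|---|
| SD 1.0, r 0.8, 80% above (λ = 0.350) | 0.2 × 1.0 × 0.350 = 0.070 | 7% |
| SD 1.0, r 0.65, 50% above (λ = 0.798) | 0.35 × 1.0 × 0.798 = 0.279 | 24% |
| SD 1.5, r 0.5, 30% above (λ = 1.159) | 0.5 × 1.5 × 1.159 = 0.869 | 58% |

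**What a fresh baseline would remove.** If correlation decays with time, a fresh baseline in a selected patient also falls somewhat by the later samples. The removable part then depends on the correlation between eligibility and baseline. Assume 0.8 for that and 0.65 to later values, with c = 0.5:

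- SD 0.8: 0.2 × 0.8 × 1.141 = 0.183, or 17%;
- SD 1.2: 0.2 × 1.2 × 1.141 = 0.274, or 24%.

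So 17% to 24% is removable, out of an apparent 27% to 38%. With a constant correlation, as in set B, all of it is removable.

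**Chance that a diet looks better than baseline with no effect.** Under set B, with each diet's two end-of-period values averaged, simulation gives 55% to 78% when the baseline is substituted (middle case 66%). A fresh sample gives 50% if errors at screening and baseline are independent.

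**Pooled estimate.** The log bias scales with the share of baselines substituted, which is not given. In set B's middle case the apparent fall in the group geometric mean is 1 − exp(−0.05 × 0.279) = 1.4% at a 5% share, 2.8% at 10%, 5.4% at 20% and 8.0% at 30%.

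**The case against.** **The fallback may mean only that the same datum is retrieved from another record.** Site email fits that reading, and the paragraph follows a list of registry fields. Section 3.4 also defines the baseline period, and an eligibility value falls outside it. This reading is possible, but the text does not state it: it speaks of any measure in Table 1 and names the form that holds the eligibility result.

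**Other rules already cover a missing sample.** Section 3.4 holds a participant back from the next treatment block until stool is collected and sent. Section 3.5.4 drops someone who never sends a specimen. Section 3.6.2 ignores missing outcomes in individual trials. These make the problem uncommon, and that stands. They do not close the route: the hold requires a sample to be sent, not a usable result; 3.5.4 words it as between treatment periods; and 3.6.2 does not say whether values are ignored before or after replacement.

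**Not every substituted value was selected.** This stands. Patients admitted on lactoferrin, CRP or ESR, or case by case, may have no eligibility calprotectin or one that was not chosen for being high. With uncorrelated errors, the middle-case regression bias is then zero; it is 0.14 log units if the errors correlate at 0.5.

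**The separate analysis plan may settle it.** Section 3.6.2 announces one. It is not in the reviewed text, so a baseline rule may exist there.

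A reader might also infer that clinician disease activity is inflated in the same way. The documents do not support this. Section 3.5.2 excludes only severe scores (SPCDAI above 45, PUCAI above 60), so entry scores are capped from above and regression would work against apparent improvement.

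**Conclusion.** The point holds for baseline fecal calprotectin. As written, the fallback permits the substitution, and the bias direction is clear where calprotectin was the qualifying marker. The per-patient size, 7% to 60% across both sets, rests wholly on assumed variability, correlation and cut-off. Part of the upper end would remain with a fresh baseline if correlation decays over time.

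It would go too far to conclude that the trial's pooled diet-versus-usual-diet estimate is materially overstated. The share substituted is unknown, could be zero, and is probably small. Nor is the comparison of SCD with modified SCD at risk, since both diets are set against the same baseline. The matter deserves correction because an affected patient's own report carries the full bias and the remedy is nearly free.

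**What to change.** Add after the fallback sentence under Outcome Measures:

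> This does not apply to fecal calprotectin. Baseline fecal calprotectin is only the study stool sample collected between enrollment and the start of the first diet. If that sample gives no usable result, the baseline is treated as missing under Missing data in section 3.6.2. The diet-versus-baseline calprotectin result is then not shown to that patient, and the pooled model handles the baseline as missing.

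This defines the baseline by sample, so the result of that same sample found in another record remains the same measurement. It also settles how the fallback and the missing-data rule fit together for this outcome. Keep the fallback for demographics, medications and disease characteristics. No separate rule for clinician disease activity is needed on this ground.

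The cost is a few sentences of protocol and analysis-plan wording, and the loss of a diet-versus-baseline calprotectin result for a few patients.
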